10.1 Study Endpoints

This is a phase II open label study to identify baseline and/or pharmacodynamics biomarkers of clinical response to BYL719 based on quantitative change in tumor size following 10-21 days of neoadjuvant BYL719 in patients with operable HNSCC. Δ Tumor size will be treated as a continuous variable, based upon the percent change in RECIST-determined index lesions pre and post-treatment.

10.2 Determination of Sample Size and Accrual Rate

10.2.1 Sample Size and Power Estimate

The primary objective of the study is to identify baseline and/or pharmacodynamic biomarkers that might have predictive utility to determine the clinical response to BYL719. The overall sample size is 14 evaluable patients. Accrual will continue until 14 evaluable patients have enrolled. If patient had baseline tissue samples obtained, has taken at least 10 doses of drug, and has undergone response assessment that is of sufficient quality to assess the primary clinical and biomarker endpoints, they are evaluable. Based upon prior window trials, up to 20 patients will be enrolled to meet these criteria. The sample size is based upon the following considerations: half of enrolled patients will demonstrate genomic PI3K pathway activation, defined as PIK3CA mutation or amplification, or PTEN deletion. We expect those with genetically activated PI3K to demonstrate a median Δ Tumor size of (-)20%, whereas those with no genomic PI3K activation to demonstrate a median increase of (+)5%. Alpha is set to 0.03 and beta is set to 0.20.

As a biomarker study, the statistical design is to accrue a sufficient number of patients and provide 80% power to test one or any of 5 key hypotheses with individual alphas of 0.03: 1) relationship between Δ Tumor size and baseline genomic *PIK3CA* activation; 2) relationship between Δ Tumor size and change in expression of HPV mRNA (qPCR); 3) relationship between Δ Tumor size and change in expression of E6, E7 oncoprotein (immunoblotting); 4) relationship between Δ Tumor size and change in expression of phospho-HER3 (immunoblotting and RPPA); 5) relationship between Δ Tumor size and change in expression of HER3/PI3K dimers (Monogram). 14 patients with complete biomarker data are needed to achieve 80% power for the 5 primary hypothesis and limit overall family wise error rate (FWER) to 15%. Based upon prior window trials, accounting for treatment compliance and quality paired tumor specimens, this will require enrollment of 20 patients.

As an example, to justify the sample size for the first key hypothesis (relationship between Δ Tumor size and baseline genomic *PIK3CA* activation), the standard deviation of Δ Tumor size

was estimated from the erlotinib arm of [name] previously completed study of erlotinib and dasatinib or both versus placebo (Bauman JE et al, JCI Insight 2017). In this study, the quantitative change in tumor size after 10-21 days of targeted therapy ranged from -30% to 55%. Assuming the same standard deviation for the change in tumor size after BYL719 treatment as observed for the erlotinib arm ($sd = 8\%$), the study will have $> 90\%$ statistical power to detect the mean difference of -20% versus +5% in those with and without *PIK3CA* activation, assuming an alpha level of 0.03. The power was calculated based on a two-sample *t* test with equal variances, assuming an alpha level of 0.03 with $n = 7$ per group.

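### Do the sample-size inputs in section 10.2.1 contradict the 14 evaluable patients they are said to support?

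*Combined protocol and SAP*

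**What the plan says.** Section 10.2.1 fixes the size at 14 evaluable patients, with up to 20 enrolled. It gives the basis as "The sample size is based upon the following considerations: half of enrolled patients will demonstrate genomic PI3K pathway activation", followed by the expected effect: "We expect those with genetically activated PI3K to demonstrate a median Δ Tumor size of (-)20" percent in the activated group, against a 5% increase in the rest. It then states "Alpha is set to 0.03 and beta is set to 0.20". No SD appears at this point.

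The next paragraph widens the basis. It lists five hypotheses, each at alpha 0.03: the *PIK3CA* comparison and four relations between change in tumor size and change in a marker. It says that "14 patients with complete biomarker data are needed to achieve 80% power for the 5 primary hypothesis", with a family-wise error rate of 15%.

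The last paragraph opens with "As an example, to justify the sample size for the first key hypothesis". It takes its SD from an earlier window study, "Assuming the same standard deviation for the change in tumor size after BYL719 treatment as observed for the erlotinib arm", and the value is 8%. With 7 per group and alpha 0.03 it reports more than 90% "statistical power to detect the mean difference of -20% versus +5% in those with and without" *PIK3CA* activation. The method is given: "The power was calculated based on a two-sample *t* test with equal variances". Sidedness is not given.

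**The concern.** The considerations listed as the basis for 14 (even split, -20% versus +5%, alpha 0.03, beta 0.20) all belong to hypothesis 1, and the only missing input is the SD. The example gives that SD, expressly to justify the size for hypothesis 1. A reader who joins the two expects 14 to come out, and it does not.

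Working backwards, 14 is the smallest equal-group total with 80% power only if the SD is well above 8, and at such SDs power with 14 is below 90%. That suggests a choice: either a larger SD set 14 and the quoted power is too high, or the SD of 8 stands and the listed inputs did not set 14.

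The stakes would be the credibility of the power claim for a primary objective and the reason for enrolling 20 patients who are awaiting potentially curative surgery.

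**Working it through.** **Inputs, all from section 10.2.1.** Difference 5 - (-20) = 25 points; SD 8; alpha 0.03; equal groups; equal-variance two-sample t test. The effect is called a median in one place and a mean in another; the two are taken as equal, with normal data. Because sidedness is not stated, both versions were run.

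**Formula.** With n per group, degrees of freedom are 2n - 2 and the noncentrality is 25 / (SD × √(2/n)). Power is the probability that a noncentral t variable exceeds the critical value.

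**The plan's own figure.** For n = 7 and SD 8, the noncentrality is 25 / (8 × √(2/7)) = 5.85. The two-sided critical value on 12 degrees of freedom is 2.46, and power is 99.9%. The claim of more than 90% is correct, though loose.

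**Power at SD 8 for smaller groups.**

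| n per group | Total | Two-sided | One-sided |
|---|---|---|---|
| 3 | 6 | 69.3% | 84.9% |
| 4 | 8 | 90.7% | 96.6% |
| 5 | 10 | 97.6% | 99.3% |
| 6 | 12 | 99.5% | 99.9% |
| 7 | 14 | 99.9% | >99.9% |

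The smallest equal-group total for 80% power is 8 two-sided or 6 one-sided. An exact rank-sum test also needs 8 (about 86 to 87% at 4 v 4, by simulation). Hypothesis 1 at SD 8 therefore does not yield 14 by any of these routes.

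**The back-solved SD.** Seven per group is the minimum for 80% power when the SD lies between 12.63 and 13.97 (two-sided) or 14.45 and 15.88 (one-sided). Power with 14 over those ranges is 88% down to 80%, and 87% down to 80%. No such SD is stated anywhere in the document. The calculation also presumes that 14 was chosen as the exact minimum for this one test, which the plan does not say.

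**How much room 14 leaves (two-sided).**

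| SD | 4 v 4 | 7 v 7 |
|---|---|---|
| 8 | 91% | 99.9% |
| 10 | 74% | 98% |
| 12 | 58% | 91% |
| 13 | 51% | 86% |

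With 14 patients, 90% power holds up to an SD of 12.17 and 80% up to 13.97. At SD 8, even a 2 v 12 split gives 93%.

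**The other hypotheses.** If hypotheses 2 to 5 were tested as Pearson correlations (an assumption; the plan names no test), 14 patients would give 80% power at two-sided alpha 0.03 for a correlation of about 0.71. At 0.5, power would be about 38%. So one of these could need 14 or more, but the section gives no effect size with which to check.

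**Error rate.** 5 × 0.03 = 0.15, matching the stated 15%; if the tests were independent it would be 1 - 0.97^5 = 0.141.

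**The case for a change.** The strongest case for acting is that the section presents a basis and the basis does not produce the number. If 14 came from hypothesis 1 at beta 0.20, some other SD was used and the power above 90% does not belong with it. If 14 came from hypotheses 2 to 5, nothing is given to support the claim of 80% power on all of them. The source study's reported range of -30% to 55% spans 85 points, more than ten SDs at 8, so a larger SD is possible. And at the plan's own 14-of-20 yield, 8 evaluable patients would mean enrolling 8 / 0.7 = 11.4, or 12.

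The traceability part of this stands: the section does not show how 14 was reached.

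The rest does not carry. The range may cover all arms of that study, so it does not contradict an SD of 8 in one arm. Doubt about the SD also argues for keeping 14, since 8 patients fall to 74% power at SD 10. The patients beyond 8 do have a stated purpose, although it is not quantified: section 10.2.1 ties 14 to five hypotheses, and section 10.2.2 requires 14 patients with tumor and biomarker measurements at both times. A null *PIK3CA* result will be read from the observed difference, SD and confidence interval, not from the SD that set the size.

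**Conclusion.** No change to the plan. An 80% target across five hypotheses and power above 90% on one of them, given as an example, can both be true of the same 14 patients. The quoted power is right at its stated SD (99.9% two-sided), and no stated figure is shown to be wrong. Filling in the derivation would leave the sample size, alpha, test and conclusions unchanged.

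Two tempting edits would make the section worse. Replacing the power claim with 80 to 88% would rest on an SD that appears nowhere in the document. Writing that 8 patients suffice would put a more fragile number in place of one that tolerates an SD up to about 12 with 90% power.

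What remains is a minor documentation gap: the inputs that set 14, the sidedness, and effect sizes for hypotheses 2 to 5 are not written down. The figures here assume normal data, equal variances and groups of equal size unless noted; the totals of 8 and 6 depend on whether the test is two-sided or one-sided. Under either, hypothesis 1 is more than adequately powered at the plan's own inputs.

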2.3.2 Secondary Endpoints

[figure not shown]
- Safety. The safety of this window intervention will be reported descriptively, including tabulation of toxicities according to NCI CTCAE v.4.03, surgical complications, and length of hospital stay.
- Mechanistic biomarker endpoints. Changes in pre- and post-treatment tumor levels of:
 - HPV mRNA (qPCR) – laboratory of [name] (UNM). We hypothesize that BYL719 will reduce HPV mRNA, and this will correlate with decrease in tumor size.
 - E6 and E7 oncoproteins – laboratory of [name] (UNM). We hypothesize that BYL719 will decrease tumoral E6 and E7 oncoprotein levels, and this will correlate with decrease in tumor size
 - Phospho-HER3 – laboratory of [name] (UCSF). We hypothesize that pHER3 is a resistance mechanism for BYL719, and that pHER3 will be upregulated in non-responders.
 - HER3/PI3K dimers (Monogram). We hypothesize that HER3/PI3K dimerization is a resistance mechanism for BYL719, and that dimers will be upregulated in non-responders.

3 Study Design

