Appendix 5 Tumor Biomarkers

Tumor tissues obtained before treatment with BYL719 will be assessed for canonical *PIK3CA* mutations by SNaPshot PCR(60) and amplifications by FISH.(53) *PTEN* loss will be assessed by FISH.(53) In addition, we will assess *PIK3CA* mutations using a comprehensive full length sequencing approach covering 202 cancer associated genes to ultradeep depth developed as part of the SU2C PI3K in women project.(53) We will assess HPV viral load and levels of HPV E6 and E7 transcripts in paired, pre- and post-treatment tissues by RT-qPCR. We will assess HPV viral load by qPCR and levels of HPV E6 and E7 transcripts by RT-qPCR in paired, pre- and post-treatment tissues. We will also assess paired tumor cell lysates for expression of total and phosphorylated signaling proteins using reverse phase protein array (RPPA), a high-through-put quantitative proteomics platform to detect changes in signaling events.

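### Do the two-part hypotheses on E6/E7 and phospho-HER3 undermine the alpha of 0.03 per hypothesis and the 15% family-wise limit?

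*Combined protocol and SAP*

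**What the plan says.** Section 10.2.1 sets out five hypotheses, each relating change in tumor size to one biomarker: genomic PIK3CA activation (H1), HPV mRNA (H2), E6/E7 oncoprotein (H3), phospho-HER3 (H4) and HER3/PI3K dimers (H5). The design is to "test one or any of 5 key hypotheses with individual alphas of 0.03", and the stated aim is to "limit overall family wise error rate (FWER) to 15" percent. The same section says that "14 patients with complete biomarker data are needed to achieve 80% power for the 5 primary hypothesis".

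H3 is worded as "change in expression of E6, E7 oncoprotein (immunoblotting"), which is two proteins on one assay. H4 is worded as "change in expression of phospho-HER3 (immunoblotting and RPPA"), which is one protein on two assays. H2 and H5 each name one measure.

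Other sections touch on these biomarkers:

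- Section 2.3.2 lists them as secondary mechanistic endpoints. It expects that "BYL719 will decrease tumoral E6 and E7 oncoprotein levels", without choosing between the two proteins, and it gives no assay for phospho-HER3.
- Section 10.2.2 ties replacement of patients to having at least one of five biomarkers of interest, measured at both time points.
- Appendix 5 describes "levels of HPV E6 and E7 transcripts by RT-qPCR in paired, pre- and post-treatment tissues" and "expression of total and phosphorylated signaling proteins using reverse phase protein array (RPPA"). It does not mention immunoblotting.
- The Biomarker Assessments row of the synopsis lists phospho-HER2 where section 10.2.1 has phospho-HER3.

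**The concern.** A family-wise limit means something only if the number of tests is fixed. Read literally, the list in section 10.2.1 contains seven measures, while the 15% is built on five tests. If an analyst tested E6 and E7 separately at 0.03 and called H3 positive when either succeeded, the error for H3 would be above 0.03. The same holds for H4 if immunoblot and RPPA each had a chance. A rule that both must succeed protects the error but gives less power than a single measure. Since the text does not choose, the choice could in principle be made after the results are known.

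The differences between sections add to the doubt. The synopsis names another receptor, and Appendix 5 lists E6/E7 transcripts where H3 needs protein. It is also not spelled out whether a patient with E6 but not E7, or with RPPA but no immunoblot, has complete biomarker data.

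**Working it through.** **Inputs from section 10.2.1:** five hypotheses, alpha 0.03 each, family-wise limit 15%, power 80%, 14 evaluable patients. The H1 example uses means of -20% and +5%, SD 8% and 7 patients per group.

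**Inputs assumed:** a two-sided Pearson test for H2 to H5, and the correlation between the two measures within H3 or H4. The documents give neither.

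**1. The plan's own figure.** The Bonferroni sum is 5 x 0.03 = 0.15, which matches. With independent tests it is 1 - 0.97^5 = 0.141. The stated limit therefore holds when each hypothesis spends 0.03 in total.

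**2. H1.** A two-sample t test with 7 per group, a difference of 25, SD 8 and two-sided alpha 0.03 has power 99.9%. This agrees with the stated figure of more than 90%. H1 has one measure and is untouched by the question.

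**3. If either measure could count at 0.03.** The bound for one hypothesis is 2 x 0.03 = 0.06; with independent measures it is 1 - 0.97^2 = 0.059. Simulation at n = 14 gives:

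| Assumed correlation within the pair | Error for the hypothesis |
|---|---|
| 0 | 5.9% |
| 0.5 | 5.6% |
| 0.8 | 5.0% |
| 0.9 | 4.5% |
| 0.99 | 3.5% |

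Over the family, seven tests have a bound of 7 x 0.03 = 0.21 (1 - 0.97^7 = 0.192 if independent). Simulation gives about 12% to 19%, depending on the correlations assumed within and between hypotheses, so the range lies on both sides of 15%. Five tests on the same basis give about 11% to 14%.

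**4. Rules that respect the allocation.**

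- *One measure per hypothesis:* error 3.0%. The detectable correlation with tumor change at 80% power is 0.705.
- *Both measures required:* error at or below 3%. At a true correlation of 0.705, power is 66% to 78% for within-pair correlations from 0.5 to 0.99.
- *Split of 0.015 + 0.015:* the total is 3 x 0.03 + 4 x 0.015 = 0.15. Power for each component falls from 80% to 71%.

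**5. The sections side by side.**

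- *Phospho-HER2:* the secondary objectives and the design panel of the same synopsis say pHER3, as do sections 2.2, 2.3.2 and 10.2.1. The single contrary entry is a slip.
- *E6/E7 transcripts in Appendix 5:* these correspond to H2 (HPV mRNA), so they are not a competing definition of H3.
- *Immunoblotting absent from Appendix 5:* the appendix also leaves out HER3/PI3K dimers, which are H5, and Ki-67, which is in section 2.2. It is not a full list of assays, so its silence contradicts nothing. Its RPPA entry agrees with H4.

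**The case for a change.** The best argument for a change is that section 10.2.1 itself calls these hypotheses key and primary, and attaches an alpha, a power and a family-wise limit to them. A lenient 15% does not excuse leaving a test undefined. Unless two measures are perfectly correlated, letting either count at 0.03 takes the hypothesis above 0.03. Requiring both, or splitting, takes power below that of one measure. Only one named measure keeps both figures, and naming it costs a sentence.

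The arithmetic stands, and so does the observation that no section names the measure or the rule. Three things weaken the conclusion:

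- The seven-test case is a construction that no section proposes. Both sections that count, 10.2.1 and 10.2.2, count five.
- The size of the effect rests on inputs the plan does not give. H2 to H5 have no stated test or effect size, so the 80% is not tied to a particular measure. For H4 the two measures are the same protein on two platforms, where high correlation is plausible and the excess error is smallest.
- Tightening the meaning of complete data is not clearly free. Section 10.2.2 appears to accept a patient with at least one of the five biomarkers. Demanding a named measure for every hypothesis could force more replacements within the 20 planned enrolments.

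**Conclusion.** The ambiguity is real but does not call for a change. As written, the plan gives 0.03 to each of five hypotheses, and that allocation meets its 15% limit. An analyst who keeps to it can use one measure, require both, or divide the 0.03, and stays within the limit in each case. Error above 0.03 for H3 or H4, never more than 0.06, arises only under an either-counts rule that the documents do not adopt, and even then the 15% is not shown to be exceeded. A rewrite would record a choice already bounded by the stated alpha; it would not bring in a better method. The setting also limits the stakes: this is a single-arm window study with 14 evaluable patients, section 2.3.1 makes tumor change and its difference by PIK3CA pathway status the primary endpoints, and E6/E7 and phospho-HER3 are secondary in section 2.3.2.

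This conclusion rests on reading the 0.03 as the total for each hypothesis, which is the reading under which the plan's sum of 0.15 works. The percentages for the alternative rules depend on the assumed Pearson test and correlations.

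### Testing all five hypotheses at a fixed 0.03 is valid Bonferroni at 15%, but Holm's step-down at the same 15% would be more powerful at almost no cost

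*Combined protocol and SAP*

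**What the plan says.** Section 10.2.1 lists five key hypotheses, all about change in tumor size. Hypothesis 1 relates it to baseline genomic PIK3CA activation. Hypotheses 2 to 5 relate it to changes in HPV mRNA, E6/E7 oncoprotein, phospho-HER3 and HER3/PI3K dimers.

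The error rates are set out in three places in that section:

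- The design is to "test one or any of 5 key hypotheses with individual alphas of 0.03".
- The aim is to "limit overall family wise error rate (FWER) to 15" percent.
- In general, "Alpha is set to 0.03 and beta is set to 0.20".

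On power, it states that "14 patients with complete biomarker data are needed to achieve 80% power for the 5 primary hypothesis". Only hypothesis 1 has a worked calculation: a two-sample t test to "detect the mean difference of -20% versus +5% in those with and without" PIK3CA activation, with a standard deviation of 8% taken from an earlier erlotinib arm, "assuming an alpha level of 0.03 with $n = 7$ per group". The stated result is power above 90%.

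No step-down, ordered or other adaptive multiplicity procedure appears anywhere in the document.

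**The concern.** A fixed 0.03 for each of five tests holds the family error at 15% whatever the results. Once one hypothesis has been rejected, however, only four remain that could yield a false rejection, and a step-down rule can test them at a less strict level without exceeding 15%. The current rule does not use that room.

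Hypotheses 2 to 5 are where this matters. They are tested in 14 patients, and the plan shows no calculation behind the 80% power claimed for them. Hypothesis 1 is well powered on the plan's own inputs, so under Holm its rejection would usually move the other four to a threshold of at least 0.0375. What is at stake is some power for the marker hypotheses, not the validity of the trial.

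**Working it through.** **1. The plan's own figures.** Family error: 5 × 0.03 = 0.15, which matches the stated 15% exactly. Independent tests would give 1 − 0.97⁵ = 0.141, so the plan's figure is the Bonferroni sum.

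Hypothesis 1: difference 25 points, SD 8, n = 7 per group, two-sided α = 0.03 (sidedness is not stated; two-sided is assumed throughout).
- Noncentrality: (25/8) × √(7/2) = 5.85 on 12 degrees of freedom
- Critical t: 2.461
- Power: 99.9%, consistent with the stated figure of above 90%

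**2. Holm at 15%.** Order the five p-values and compare the k-th smallest with 0.15/(6 − k), stopping at the first failure. For a Pearson test with n = 14, the critical |r| is t/√(t² + 12).

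| Step | Threshold | Critical \|r\| |
|---|---|---|
| 1 | 0.15/5 = 0.03 | 0.579 |
| 2 | 0.15/4 = 0.0375 | 0.559 |
| 3 | 0.15/3 = 0.05 | 0.532 |
| 4 | 0.15/2 = 0.075 | 0.490 |
| 5 | 0.15/1 = 0.15 | 0.406 |

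Every threshold is at least 0.03, so no rejection made by the fixed rule is lost. Holm controls the family error at 15% under any dependence. That is needed here, because all five tests share one outcome.

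**3. Size of the gain.** The plan gives no effect size, SD or test for hypotheses 2 to 5, so these inputs are assumptions: Pearson tests, equal true correlation ρ for each real marker, and markers independent of one another given tumor change. Hypothesis 1 is as planned with SD 8%. Each setting used 40,000 simulated trials.

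| Setting | Fixed 0.03 | Holm at 15% |
|---|---|---|
| One real marker, ρ = 0.6: its power | 61% | 66% |
| Four real markers, ρ = 0.3: average power | 13% | 18% |
| Four real markers, ρ = 0.5: average power | 40% | 55% |
| Four real markers, ρ = 0.6: average power | 61% | 79% |
| Four real markers, ρ = 0.7: average power | 83% | 95% |

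No rejection was lost in any trial. With all five nulls true, the family error was about 14% under both rules.

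**4. What does not change.** Holm's first threshold is also 0.03, so the chance of at least one rejection is identical under the two rules.

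**5. What it costs in false positives.** Hypothesis 1 real, real markers at ρ = 0.6:

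| Real markers | Rate per null marker, fixed → Holm | Any false marker, fixed → Holm |
|---|---|---|
| One | 3% → about 4.7% | about 9% → 13% |
| Two | 3% → about 6.4% | about 6% → 12% |
| Three | 3% → about 10% | 3% → about 10% |

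All the family error rates stay below 15%.

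**6. Sensitivity to the SD.** If the SD exceeds 8%, hypothesis 1 is rejected less often and opens the later steps less often. At assumed SDs of 15% and 20%, its power at 0.03 is about 74% and 48%, and the one-marker gain falls from about 5 points to about 3 and 2. With four real markers at ρ = 0.6 and SD 16%, average power still rises, from 60% to 74%.

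**The case against.** The strongest reply is that nothing here is wrong. The plan names its family, its per-test level and its family error, and the three agree. Bonferroni is a legitimate pre-specified choice in a study of this size. That stands.

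A second reply is that the fixed rule does buy something. It holds each marker's false-positive rate at 3% whatever happens to the others, and in a screen for predictive markers a sponsor may want that. This also stands. A reader might infer that the fixed 0.03 gives no protection in return for the lost power, but that is true only of the nominal 15% bound. The plan also states 0.03 as a level for each hypothesis, and Holm gives that up.

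A third reply is that if the goal is to detect at least one of the five, Holm adds nothing. That is correct on that reading. The same section also claims 80% power for all five hypotheses, and on that reading the gain is relevant.

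A reader might also infer that the plan treats rejection of hypothesis 1 as nearly certain. The text claims only more than 90%. The 99.9% follows from an SD of 8%, and the same section reports changes from −30% to 55% in the earlier study, without saying that this range belongs to the erlotinib arm alone.

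Finally, the set of p-values is not fully defined. Hypothesis 3 covers E6 and E7, and hypothesis 4 names both immunoblotting and RPPA. Seven separate tests at 0.03 would sum to 0.21. This affects both rules equally, so it does not defeat the suggestion, but the new sentence has to settle it.

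**Conclusion.** The point holds as an efficiency improvement. Section 10.2.1 uses valid single-step Bonferroni, and Holm at the same 15% is uniformly at least as powerful. At ρ = 0.6 the gain for hypotheses 2 to 5 runs from about 5 points with one real marker to about 18 points on average with four. It is about 5 points with four weak markers (ρ = 0.3).

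These sizes rest on assumed correlations, Pearson tests and the planned SD of 8%. The larger ones also need all four markers to be real. The documents support neither a claim that the plan's error control is faulty nor a claim that the larger gains are to be expected. The sample size of 14 and the hypothesis 1 power statement are unaffected.

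**What to change.** In Section 10.2.1, replace the clause that gives each hypothesis its own 0.03 with: *the five p-values, one pre-specified per hypothesis, are tested by Holm's step-down procedure at a family-wise error rate of 15%.* Keep 0.03 as the first-step level, so that the hypothesis 1 power statement still reads correctly. Name the single p-value for hypotheses 3 and 4.

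The change needs no patients or assays and leaves the nominal 15% as it is. Its cost is the higher false-positive rate per null marker shown above, which the sponsor should accept knowingly. If 3% per marker is wanted for its own sake, keep the present rule and say so. Either way, the choice must be made before results are known, because a later switch would be data-driven.
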